3.0 Study population

3.1 Inclusion and exclusion criteria

Inclusion criteria

COPD diagnosis with QoF approved read codes

Age \geq 40 years

Patients have one year of practice data prior COPD diagnosis and 2 years of practice data after COPD diagnosis

Spirometry data supportive of a COPD dx in the 5 year window around date of diagnosis.

Patients must be diagnosed within the last 15years

Exclusion criteria

Patients aged less than 40 at diagnosis

No valid spirometry data available

Patients diagnosed earlier than 1997

Table 1: Inclusion and exclusion criteria

3.2 Data source

The study will use patient data from the Optimum Patient Care Research Database (OPCRD). The study team work with fully anonymised data, removed of any patient identifiable information. The OPCRD is developed, maintained and owned by Optimum Patient Care, a social enterprise company that aims to improve patient outcomes through medical research and services. OPC provides evidence based recommendations to UK general practices through bespoke software and practice reports.

The OPCRD currently comprises longitudinal medical records for over 2.2 million patients from over 550 primary care practices across the UK. The OPCRD contains two types of data:

- routinely recorded clinical data and
- questionnaire responses from over 40,000 respiratory patients.

The OPC questionnaires are a compilation of validated questions covering symptoms, disease control, triggers, side effects, quality of life and unique adherence measures. Indeed the OPCR is the only database in the UK which compliments routinely recorded disease coding and prescribing information with patient reported outcomes. OPCR also links with nationwide practice prescribing data to enable targeted delivery of dataset needs.

The database has received a favourable opinion from the Health Research Authority for clinical research use (REC reference: 15/EM/0150). It is governed by The Anonymous Data Ethics Protocols and Transparency (ADEPT) committee, an independent body of experts and regulators commissioned by the Respiratory Effectiveness Group (REG) to govern the standard of research conducted on internationally renowned databases. All research using OPCR will be registered on recognised study databases such as the European Network of Centres for Pharmacoepidemiology and Pharmacovigilance (ENCePP).

4.0 Study variables and study outcomes

4.1 Demographic and baseline variables

Refer to Appendix for mock tables of demographic and baseline variables.

4.2 Primary outcome

Predictors of initial treatment patterns

Primary outcome will identify predictors of GP prescribing behaviour when treating newly diagnosed COPD patients with their first pharmacological therapy. It will assess the odds of being prescribed:

- any initial COPD therapy vs.
- no COPD therapy

A further analysis will be conducted in regard to the odds of being prescribed:

- maintenance therapy versus
- short-acting agents/no therapy

4.3 Secondary and exploratory outcomes

Initial treatment patterns

To obtain the data required for exploring the primary outcomes, exploratories will be conducted to investigate the distribution of COPD pharmacological therapy in the main potential predictors (see appendix for full list). Results will be summarised and tested using chi-square to identify whether variation occurs among the categories.

5.0 Statistical analysis

5.1 Software used and power calculation

Baseline patient characteristics and outcome analysis (Logistic Regression) will be carried out using SPSS version 20², SAS version 9.3 and Microsoft Office EXCEL 2007.

5.2 Significance testing

Statistically significant results will be defined as $p < 0.05$ and trends as $0.05 \leq p < 0.10$.

5.3 Baseline characterisation

Summary statistics will be produced for all baseline and outcome variables (see appendix), as a complete dataset and by treatment groups. For variables measured on the interval or ratio scale, these will include:

- Sample size (n)
- Percentage non-missing
- Mean
- Variance / Standard Deviation
- Range (Minimum / Maximum)
- Median
- Inter-quartile Range (25th and 75th percentiles)

For categorical variables, the summary statistics will include:

- Sample size (n)
- Range (if applicable)
- Count and percentage by category (distribution)

5.4 Analysis of study outcomes

COPD initial treatment patterns

Logistic regression analysis for all patients receiving first COPD therapy. This analysis will be conducted on:

- a. All patients receiving first COPD therapy
- b. The subgroup of patients who receive their first therapy on their date of COPD diagnosis

This will be carried out as follows:

Investigate the COPD therapy distribution of by the following main potential predictors:

- a. Year of initial COPD diagnosis (1997-2001; 2002-2006; 2007-2010)
- b. Presence of co-morbid asthma diagnosis
- c. Lung function grade (please note that GOLD stage 2 will be used as the reference). This will also be repeated for the earlier analysis investigating predictors of initial therapy choice for all patients receiving first COPD therapy
- d. mMRC score
- e. Annual exacerbation rates
- f. GOLD group with the following comparisons:
 - B vs A
 - D vs C
 - A+B vs C+D

For each potential predictor consider:

- the distribution of initial COPD therapy (number and percentage of patients and bar chart) will be summarised
- Need to test to see if it varies among the categories of each potential predictor with a chi-square.

Predictors of initial COPD treatment

Evaluate how the potential predictors outlined above could affect the choice of initial COPD therapy in terms of:

a. Odds of being prescribed any initial COPD therapy vs. no therapy

For each potential predictor:

- The distribution of initial COPD therapy (yes/no) (number and percentage of patients and bar chart) will be summarised and a test to see if it varies among the categories of each potential predictor with a chi-square will be completed.
- Odds ratios (ORs) with their 95% confidence intervals (CIs) will be calculated using an univariable logistic regression model and a multivariable logistic regression model with stepwise reduction to derive best-fitting model of non-collinear predictors
- Presence of co-morbid asthma diagnosis used both as adjustment and as stratification variable (two multivariable models)
- Collinearity analysis on all potential predictors and confounders

b. Odds of receiving initial COPD maintenance therapy vs. short-acting agents/no therapy

For each potential predictor:

- The distribution of initial COPD maintenance therapy (yes/no) (number and percentage of patients and bar chart) will be summarised and tested to see if it varies among the categories of each potential predictor with a chi-square.
- Odds ratios (ORs) with their 95% confidence intervals (CIs) will be calculated using an univariable logistic regression model and a multivariable logistic regression model with stepwise reduction to derive best-fitting model of non-collinear predictors
- Presence of co-morbid asthma diagnosis used both as adjustment and as stratification variable (two multivariable models)
- Collinearity analysis on all potential predictors and confounders

Refer to Appendix for mock tables of secondary/exploratory outcome results.

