Study Protocol

Predictors of treatment choice in patients with COPD

A retrospective observational cohort study that investigates predictors of initial treatment choice in COPD patients.

Date:

01/02/2014Novartis

Research in Real-Life Pte Ltd
[name]
[name]
Singapore
[name]

Research in Real-Life Ltd
[name]
United Kingdom

Phone [[name]]
Fax ([contact]
Web site <http://www.rirl.org>

Chief Investigator:

[name], Professor of Primary Care Respiratory Medicine and RIRL Director

[contact]

Office number: [name]

Skype ID: [name]

Email: [contact]

Project coordinator:

[name]

Research in Real-Life Ltd

[name]

Direct number: [name]

Email: [contact]

Study sponsor:

Novartis

Primary contact

[name] ([contact])

TITLE	Predictors of treatment choice in patients with COPD
Subtitle	A retrospective observational cohort study that investigates predictors of initial treatment choice in COPD patients.
Protocol version number	V1.0
Medicinal product	N/A
Product code	R04512
Study aims and objectives	
This study aims to examine the changes in prescriptions patterns over time, in order to determine the potential driving factors behind GP prescribing for newly diagnosed COPD patients.
 
The objective of the study is to highlight predictors over time in GP prescription of:
 
 • any initial COPD therapy vs. • no COPD therapy 
and
 
 • maintenance therapy versus • short-acting agents/no therapy
Country of study	United Kingdom
Author	RiRL UK Ltd [name] United Kingdom

Contents

1.0	Background	5
2.0	Study Overview	6
2.1	Study aims & objectives	6
2.2	Study design	6
3.0	Study population	7
3.1	Inclusion and exclusion criteria	7
3.2	Data source	7
4.0	Study variables and study outcomes	8
4.1	Demographic and baseline variables	8
4.2	Primary outcome	8
4.3	Secondary and exploratory outcomes	8
5.0	Statistical analysis	9
5.1	Software used and power calculation	9
5.2	Significance testing	9
5.3	Baseline characterisation	9
5.4	Analysis of study outcomes	9
6.0	Regulatory and ethical compliance	11
7.0	Data dissemination	11
8.0	Advisory group	12
9.0	Research team	12
10.0	Timelines	13
11.0	References	13
12.0	APPENDIX	14
12.1	Appendix 1: Definitions	14
12.2	Appendix 2: Mock baseline results tables	15

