2.0 Study Overview

2.1 Study aims & objectives

This study aims to examine the changes in prescriptions patterns over time, in order to determine the potential driving factors behind GP prescribing for newly diagnosed COPD patients.

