2.2 Study design

A retrospective observational database study using the Optimum Patient Care Research Database. The data utilised in this study ranges from 1997 – 2013. Eligible patients must have a minimum of one year of data prior to their initial date of COPD diagnosis for baseline period, and a minimum of two years of data post their initial COPD diagnosis for outcome period to assess patient characteristics and pharmacological treatment prescriptions.

Cohorts will be chosen to assess how prescription patterns have changed over time and if certain factors such as the introduction of QoF1 in 2004 and Tiotropium (LAMA) becoming licensed in UK in January 2002 influence prescribing behaviour.

Patients will be split into three cohorts based on their date of initial COPD diagnosis:

- 1997 – 2001
- 2002 – 2006
- 2007 – 2010

COPD initial therapy will be defined as pharmacological therapy prescribed during one year prior to and at the initial date of COPD diagnosis (baseline period). COPD therapies will be grouped by treatment class:

- Inhaled corticosteroid (ICS),
- long-acting β_2 -agonist (LABA),
- long-acting muscarinic antagonist (LAMA),
- short-acting β_2 -agonist (SABA),
- short-acting muscarinic antagonist (SAMA) (in single, dual or triple therapy)
- Other respiratory pharmacological therapies (theophylline)
- None (no prior baseline pharmacological therapy).

To identify possible drivers of treatment choice, analyses will be conducted in subgroups according to:

- Year of initial COPD diagnosis
- Comorbid asthma diagnosis
- Lung function grade (GOLD stage 1, 2, 3 or 4 [2])
- mMRC dyspnea scale score
- Baseline exacerbation rate.

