12.3 Appendix 3: Mock outcome results tables

		Initial Therapy		Total	p value*
		No	Yes		
Year of Initial Diagnosis	1997-2001				
	2002-2006				
	2007-2010				
	Total				
Comorbid Asthma Diagnosis	Yes				
	No				
	Total				
mMRC Score	1				
	2				
	3				
	4				
	5				
	Total				
Annual Exacerbations	0				
	1				
	2				
	3+				
	Total				
Lung Grade	I				
	II				
	III				
	IV				
	Total				
GOLD Risk	A				
	B				
	C				
	D				
	Total				

Table 3: An Example of how Baseline data by Initial Therapy Indicator will be presented

	Reference Category	Category	Odds* of being prescribed any initial therapy		
			OR (95% CI)	p-value	Overall p-value
Comorbid asthma diagnosis	NO	YES	3.88 (3.43, 4.40)	<0.001	<0.001
Lung grade	II	I	0.87 (0.78, 0.97)	0.009	0.001
		III	1.10 (1.01, 1.20)	0.038	
		IV	1.13 (0.95, 1.36)	0.174	

mMRC score	0	1	1.17 (1.05, 1.31)	0.005	<0.001
		2	1.22 (1.08, 1.38)	0.001	
		3	1.26 (1.10, 1.46)	0.001	
		4	1.40 (1.12, 1.75)	0.003	
Annual exacerbation rate	0	1	2.33 (2.12, 2.56)	<0.001	<0.001
		2	3.60 (3.03, 4.27)	<0.001	
		≥3	4.62 (3.75, 5.69)	<0.001	

Table 4: An example of how findings from logistic regression modelling will be presented

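### Section 5.4 does not carry out the period subgroups promised in 2.2, so a changing effect of lung grade, mMRC or exacerbations would be averaged into one odds ratio

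*Protocol*

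**What the plan says.** The synopsis on the protocol's title page states the objective: "The objective of the study is to highlight predictors over time in GP prescription of" any initial therapy against none, and maintenance therapy against short-acting agents or none. Section 2.1 gives the aim: "This study aims to examine the changes in prescriptions patterns over time, in order to determine the potential driving factors behind GP prescribing".

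Section 2.2 defines three diagnosis cohorts and their purpose: "Cohorts will be chosen to assess how prescription patterns have changed over time", with the 2002 licensing of tiotropium and the 2004 introduction of QoF as possible influences. It continues: "To identify possible drivers of treatment choice, analyses will be conducted in subgroups according to" five factors, the first of which is year of initial diagnosis.

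Section 5.4 sets out the analysis. Diagnosis period, "Year of initial COPD diagnosis (1997-2001; 2002-2006; 2007-2010"), is item (a) of six potential predictors. The plan is then: "Evaluate how the potential predictors outlined above could affect the choice of initial COPD therapy in terms of" the two odds comparisons. Each comparison uses univariable models and a "multivariable logistic regression model with stepwise reduction to derive best-fitting model of non-collinear predictors". Asthma is used once as an adjustment variable and once as a stratification variable. No other stratification and no interaction term is named.

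In Appendix 3, mock Table 4 has one block of results headed "Odds* of being prescribed any initial therapy". Its rows are asthma, lung grade, mMRC and exacerbations. It has no period row and no period columns.

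**The concern.** Two questions about time are possible. One is whether GPs prescribed more or less in later periods. The other is whether the factors that led them to prescribe changed in importance. The synopsis objective and the subgroup statement in 2.2 reach the second question. The models in 5.4 are built for the first.

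A period main effect describes a shift in the level of prescribing. Without a predictor-by-period term or a model fitted within each period, each remaining predictor gets one odds ratio averaged over 1997-2010. If a driver weakened or emerged after tiotropium or QoF arrived, that average may describe none of the three periods, and nothing beside it would say so. Because period can be dropped by the stepwise procedure, even its main effect may be missing from the final model.

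**Working it through.** The protocol gives no sample size, event count or period shares, so there is no stated figure to reproduce. The check has three parts.

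**1. Promise against implementation**

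| Element | Section 2.2 / synopsis | Section 5.4 | Appendix 3 |
|---|---|---|---|
| Level of prescribing by period | Yes | Chi-square; period as a predictor | Table 3, therapy by period |
| Effect of each driver by period | Subgroups by year of diagnosis; predictors over time | No interaction or period-specific model | No period columns in Table 4 |
| Stratified models | Five subgroup factors, including period | Asthma only | Not shown |

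Table 3 cross-tabulates therapy against one predictor at a time, so it cannot show a predictor's effect within a period.

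**2. What a main-effects model reports when a driver changes**

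Assumed inputs, none of them from the protocol: a binary predictor present in 30% of patients, 60% of unexposed patients treated in every period, and three periods of equal size. The model is logit(p) = a + period + b·x, fitted to expected counts.

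The unexposed odds are 0.6/0.4 = 1.5. The treated proportions among the exposed are therefore:
- OR 1.5: odds 2.25, proportion 0.6923
- OR 2.33: odds 3.495, proportion 0.7775
- OR 3.6: odds 5.4, proportion 0.8438

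| True OR by period | Single OR, equal periods | Single OR, shares 15/40/45% | Period ORs, equal periods |
|---|---|---|---|
| 2.33 / 2.33 / 2.33 | 2.33 | 2.33 | 1.00, 1.00 |
| 1.5 / 2.33 / 3.6 (rising) | 2.25 | 2.58 | 1.12, 1.23 |
| 3.6 / 2.33 / 1.5 (falling) | 2.25 | 1.99 | 0.91, 0.81 |

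A hand check with the Mantel-Haenszel estimator agrees. The exposed proportions sum to 2.3136 and their complements to 0.6864. The estimate is (0.7·0.4·0.3·2.3136)/(0.7·0.6·0.3·0.6864) = 2.25, and the order of the periods does not enter. The period odds ratios do move, but they would be read as a change in prescribing level. In this example the level among the unexposed is constant by construction.

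**3. Whether the remedy is informative**

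The example intervals in Table 4 are used only as a guide to precision. The standard error of the log odds ratio is ln(U/L)/(2·1.96). The smallest ratio of odds ratios between first and last period detectable with 80% power at two-sided 0.05 is exp[(1.96 + 0.84)·SE·√(1/s1 + 1/s2)], where s1 and s2 are assumed period shares.

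| Contrast | SE | Equal thirds | s1 = 0.15, s2 = 0.50 |
|---|---|---|---|
| 1 vs 0 exacerbations | 0.0481 | 1.39 | 1.49 |
| Grade I vs II | 0.0556 | 1.46 | 1.58 |
| Asthma | 0.0635 | 1.55 | 1.69 |
| 3 or more vs 0 exacerbations | 0.1064 | 2.07 | 2.40 |
| mMRC 4 vs 0 | 0.1139 | 2.18 | 2.56 |

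For 1 vs 0 exacerbations with equal thirds: exp(2.80·0.0481·√6) = 1.39. At that precision, a change such as 1.5 to 3.6 (ratio 2.4) would be detectable for a common contrast. For sparse categories it would be borderline, depending on the period shares.

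**The case against.** The strongest reply has four parts.

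First, a reader might infer that no change in any driver could be seen. The documents do not support that, because section 2.2 commits to driver analyses in subgroups by year of diagnosis. Read literally, that would give period-specific results. This part stands, and it makes the defect a failure to carry 2.2 into 5.4 rather than a missing intention.

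Second, asthma is a partial exception. Assume 10,000 patients in equal periods, 25% with asthma, 60/65/70% of non-asthma patients treated, and asthma odds ratios of 6.0, 4.0 and 2.5. The main-effects model reports 3.90 (95% CI 3.43 to 4.44). It would be tempting to say that the decline is hidden, but the planned asthma-stratified models would show it. Without asthma, the 2007-2010 against 1997-2001 odds ratio is (0.7/0.3)/(0.6/0.4) = 1.56 (1.38 to 1.75). With asthma it is (2.5·2.333)/(6.0·1.5) = 0.65 (0.48 to 0.87). Their ratio is 0.42, which is 2.5/6.0. This stands, provided period is kept in both models. It does not extend to lung grade, mMRC or exacerbations, because each asthma stratum still pools the periods for them.

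Third, the aim in 2.1 can be read as change in prescribing level only, and the period chi-square and period odds ratio address that. This is fair for the aim, but the synopsis objective names predictors, and 2.2 names drivers.

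Fourth, Table 4 is captioned as an example, and interactions are often left to a statistical analysis plan. Both are true. The table's layout is supporting evidence only, and its example values say nothing about whether drivers changed. However, the protocol itself fixes the model type, the selection method and the one stratification variable, and these do not match its own section 2.2.

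**Conclusion.** The point holds as an inconsistency between the synopsis objective and section 2.2 on one side and the models in 5.4 on the other. Followed as written, 5.4 answers whether the level of prescribing changed, and may allow a change in the asthma effect to be inferred indirectly. It does not show whether lung grade, mMRC or exacerbations drove prescribing differently across the three periods. The size depends on assumed inputs: with equal periods, a 2.4-fold rise and a 2.4-fold fall give the same 2.25, and with shares of 15/40/45% they give 2.58 and 1.99, with neither revealing a trend. The documents do not show that any driver did change, nor that the study has no means at all of examining change. The matter should be corrected before analysis.

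**What to change.** In 5.4, for both outcomes:
- keep diagnosis period in the multivariable model whatever the stepwise procedure selects;
- pre-specify predictor-by-period interaction terms for asthma, lung grade, mMRC and exacerbations, with the same covariate set in all periods;
- judge change over time by the interaction test, not by comparing significance between separate periods;
- report period-specific odds ratios beside the pooled one.

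State in 5.4 that this is how the year-of-diagnosis subgroups in 2.2 are carried out. In mock Table 4, add rows for period, columns for the three periods and an interaction p-value.

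The cost is wording and a wider table, with no new data. Period-specific intervals will be wider: with equal thirds, each standard error is about √3 = 1.7 times the pooled one. There will also be several more tests to interpret, and the sparse categories will be informative only about large changes.

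### Stepwise reduction can remove the adjusted diagnosis-period effect that the study sets out to estimate, and the named model has no term for practice

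*Protocol*

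**What the plan says.** The aim in section 2.1 is about time: "This study aims to examine the changes in prescriptions patterns over time". Section 2.2 gives the same reason for the three diagnosis cohorts: "Cohorts will be chosen to assess how prescription patterns have changed over time". It names the licensing of tiotropium in 2002 and the introduction of QoF in 2004 as possible influences.

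Section 5.4 lists the main candidate predictors. The first is "Year of initial COPD diagnosis (1997-2001; 2002-2006; 2007-2010"; the others are asthma, lung function grade, mMRC score, exacerbation rate and GOLD group. For each of the two outcomes it plans a chi-square test, a univariable logistic model, and then a "multivariable logistic regression model with stepwise reduction to derive best-fitting model of non-collinear predictors". No entry or removal criterion is given. One variable has a fixed role: "Presence of co-morbid asthma diagnosis used both as adjustment and as stratification variable (two multivariable models". Nothing similar is said for year of diagnosis.

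Section 3.2 describes a source holding "longitudinal medical records for over 2.2 million patients from over 550 primary care practices across the UK". Sections 5.1 and 5.4 name logistic regression and mention no practice effect or robust standard error. Section 5.2 sets significance at p below 0.05 and calls 0.05 to 0.10 a trend.

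**The concern.** The three cohorts span 1997 to 2010. Patients diagnosed in different periods may differ in severity, asthma coding and exacerbation history. The question of whether prescribing changed needs a period effect adjusted for these, reported whatever its size. A data-driven reduction reports it only if it survives, so a small or null adjusted change would disappear from the results table.

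Two further consequences follow. A term kept because it looked strong has an estimate biased away from the null, and the usual interval ignores the selection. And because the outcome is prescriber behaviour, patients of one practice are likely to resemble each other. An ordinary logistic model then understates the standard error of any predictor that also varies between practices. Both matter most for small effects, where the cut-offs in section 5.2 decide what is called significant.

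**Working it through.** **Inputs from the protocol.** Significance level 0.05 (section 5.2; taken as two-sided, in line with the 95% intervals). Year has three levels, so 2 degrees of freedom (section 5.4). Appendix 3, Table 4, an example table, gives lung grade III vs II as OR 1.10 (1.01 to 1.20), p = 0.038, and grade I vs II as 0.87 (0.78 to 0.97), p = 0.009. The protocol states no sample size, event count or power, so there is no design figure to reproduce.

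**Inputs assumed.** Removal level 0.05 or 0.10; m = 10 to 40 eligible patients per practice; outcome intraclass correlation (ICC) 0.02 to 0.10; predictor ICC 0 to 0.10.

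**1. Chance that year is dropped.** At a removal level of 0.05 this is 1 − power. At 0.10 it comes from the 2-df noncentral chi-square with the same noncentrality.

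| Power of the year term at 0.05 | Dropped at 0.05 | Dropped at 0.10 |
|---|---|---|
| 50% | 50% | 38% |
| 80% | 20% | 12% |
| 90% | 10% | 6% |

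**2. Coverage after selection.** Let Z be normal with mean μ (the true z) and variance 1, with the term kept if |Z| > 1.96. At μ = 1:
- Kept: [1 − Φ(0.96)] + Φ(−2.96) = 0.1685 + 0.0015 = 0.170.
- Kept and covering (1.96 < Z < 2.96): Φ(1.96) − Φ(0.96) = 0.9750 − 0.8315 = 0.1435.
- Coverage given kept: 0.1435 / 0.170 = 0.844.
- Mean absolute estimate relative to the truth: about 2.5.

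By simulation, coverage is 60% at μ = 0.5, 92% at 1.5, 95% at 2 and 97% at 2.8. The inflation falls to about 1.4 at μ = 2 and 1.1 at 2.8. The problem is confined to weakly supported terms.

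**3. Ignoring practice.** The approximate design effect for a covariate is 1 + (m − 1) × ICC(outcome) × ICC(predictor).
- Lowest: predictor ICC 0 gives 1.00.
- Highest: 1 + 39 × 0.10 × 0.10 = 1.39, so the standard error is multiplied by √1.39 = 1.18.

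A random-intercept simulation (300 practices, 300 replicates per setting, Monte Carlo error about 4% on the ratio) agrees broadly. The true-to-naive standard error ratio was 0.97 to 1.04, with coverage 93% to 96%, when the predictor was unclustered or practices held 10 patients. With 40 patients per practice and outcome ICC about 0.09, it was 1.14 (coverage 91%) at predictor ICC 0.10 and 1.30 (86%) at 0.30, the last lying outside the main range.

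**4. What that does to the example rows.** Grade III: SE = (ln 1.20 − ln 1.01)/3.92 = 0.0440, and z = ln 1.10/0.0440 = 2.17, p = 0.030. With rounding of the printed figures p lies between 0.017 and 0.050, which includes the printed 0.038. The row passes 0.05 once the design effect exceeds (2.17/1.96)² ≈ 1.22. At 1.39, the interval is exp(0.0953 ± 1.96 × 0.0440 × 1.18) = 0.99 to 1.22, p ≈ 0.066. Grade I: z = 2.50, and 2.50/1.18 = 2.12, p ≈ 0.034, so it stays below 0.05. The asthma (3.88) and exacerbation (2.33 to 4.62) rows stay at p < 0.001 even at a design effect of 3.

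**The case against.** Identifying predictors is a legitimate descriptive goal, and stepwise selection is a conventional tool for it. The time effect is not lost altogether: section 2.2 plans analyses by year of diagnosis, and section 5.4 gives year a chi-square test and a univariable OR. That is right, and limits the loss to the adjusted estimate. But the adjusted estimate is the one that separates changed prescribing from changed patients.

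Several stronger readings are tempting, and the protocol does not support them:

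- *All the intervals are too narrow.* The listed predictors are patient-level, the inflation runs from nil to moderate, and every ICC and practice size above is assumed. The count of over 550 practices describes the whole database, not the eligible sample.
- *The protocol assumes independent patients.* It is silent. A statistical analysis plan, not shown here, could specify clustered or multilevel standard errors.
- *Age, sex, smoking and BMI are left out.* Section 5.4 lists only the main predictors and also mentions confounders. Section 4.3 refers to the appendix for the full list, and Appendix 1 contains these variables.
- *Terms are removed by p-value, afresh in each asthma stratum.* No criterion is stated, and the text does not say whether selection is repeated by stratum. Differing covariate sets are possible, not planned.
- *Year's absence from the mock regression table shows that it will be dropped.* Year is in Table 3 and not in Table 4, but Table 4 is labelled an example.

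**Conclusion.** The point holds in limited form. Stepwise reduction is fixed in the text for both outcomes, and nothing keeps diagnosis period in the adjusted model although it carries the study's aim. The chance of losing it is about 20% at 80% power and an assumed 0.05 removal level, and smaller with more power or a looser level. Intervals after selection are unreliable only for weakly supported terms, and whether any main predictor falls there is unknown without a sample size.

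The missing practice term is the weaker half, since it is an omission that an analysis plan may fill. Its likely size is a design effect of about 1.0 to 1.4 under the assumptions above: enough to move a borderline row such as grade III across 0.05, but not to alter strong effects. Overall this is a cheap improvement, not a flaw that invalidates the study.

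**What to change.** In section 5.4, for both outcomes:

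1. Replace stepwise reduction with one pre-specified model per outcome that keeps diagnosis period, asthma, lung grade, mMRC score, exacerbations, and the Appendix 1 demographics and comorbidities. Report the period OR whatever its size.
2. Fit GOLD group in a separate model in place of its components. The protocol does not define the groups; this assumes they are built from lung grade, mMRC score and exacerbations.
3. Use the same covariates in both asthma strata, so that their ORs are adjusted alike.
4. Report practice-clustered standard errors, by GEE or a practice random intercept.

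This changes only the wording of the model, provided a practice identifier is in the extract. The cost is somewhat wider intervals, which should be affordable in a large database.
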